3.2.4 Protocol Deviations

Protocol deviations identified during site monitoring will be captured in a Protocol Deviation log and categorized as major or minor deviations based on Protocol Deviation Classification (see Appendix of the placebo-controlled SAP). The major protocol deviations occurred in the LTE period will be summarized for subjects enrolled in LTE. The major protocol deviations for all ITT subjects in the combined placebo-controlled and LTE periods will also be summarized. Major and minor protocol deviations for all ITT subjects will be listed, respectively, across the placebo-controlled period and the LTE period. All summaries for protocol deviations will be presented by LTE treatment group.

3.2.5 Study Drug Exposure and Study Drug Compliance

A summary table of study drug exposure and compliance in the LTE period will be provided. Number of infusions (aducanumab or placebo) received will be summarized as a categorical variable (categories of 1-5, 6-10, 11-15, 16-20, 21-26, 27-39, 40-52 and 53-65) as well as a continuous variable. Number of weeks on study treatment (aducanumab or placebo), calculated as $(\text{date of last dose} - \text{date of first dose} + 29) / 7$, will be summarized as a categorical variable (every 6 months for the first 2 years of LTE, and then every year) as well as a continuous variable. Percentage of study treatment taken up to the last dose, calculated as $(\text{the actual number of infusions} / \text{by the number of infusions a subject is expected to take until the date of last infusion}) * 100$, will be summarized as a continuous variable. This table will be presented by LTE treatment group. A similar table will also be provided on the placebo-controlled and LTE active treatment period in order to summarize the exposure data while subjects are on aducanumab.

Due to the use of titration regimen in the study and possible dose reduction due to ARIA, another summary table will be provided including the following information in the LTE period: number of total infusions (categories of 1-5, 6-10, 11-15, 16-20, 21-26, 27-39, 40-52 and 53-65) as well as a continuous variable, number of infusions at each dose level (1 mg/kg, 3 mg/kg, 6 mg/kg and 10 mg/kg, respectively) summarized as a categorical variable as well as a continuous variable, number of subjects with dose increase (placebo to 1 mg/kg, 1 to 3 mg/kg, 3 to 6 mg/kg and 6 to 10 mg/kg, respectively), number of subjects with dose reduction (1 mg/kg to placebo, 3 to 1 mg/kg, 6 to 3 mg/kg and 10 to 6 mg/kg, respectively), maximum

dose level received, and cumulative dose (as a continuous variable). This table will be summarized by LTE treatment group stratified by ApoE status. A similar table will also be provided on the placebo-controlled and LTE active treatment period in order to summarize the titration and dose reduction data while subjects are on aducanumab.

A listing of study drug administration records, including dose level at each infusion, cumulative number of infusions and cumulative dose will be provided for the placebo-controlled and LTE period. A listing of aducanumab lot numbers will be provided for the placebo-controlled and LTE period.

3.3 Efficacy Analysis

3.3.1 General Considerations

The analysis population for efficacy analysis is the same as the ITT population and data from both the placebo-controlled and LTE periods will be included. All efficacy analyses will be presented by LTE treatment group, i.e, late start low dose, late start high dose, early start low dose, early start high dose (analysis display A in Appendix 4.1).

The following two comparisons will be evaluated for the long-term efficacy of aducanumab:

- The early start low dose compared with the late start low dose;
- The early start high dose compared with the late start high dose.

There will be no multiple comparison adjustments.

Visit windows for mapping efficacy endpoint

For efficacy data that are summarized or analyzed by visit, data collected on all scheduled visits and all unscheduled visits will be mapped to an appropriate analysis visit using the windowing scheme shown in Table 3. If there are 2 or more assessments available in the same analysis window for a subject, the assessment that is closest to the target visit day will be used for analysis. If there are 2 or more assessments in the same analysis window with the same distance from the target visit day, the later assessment will be used.

Table 3: Visit Windows for Efficacy Endpoints

Analysis visit	Target visit day	Analysis visit window
Baseline	1	Most recent non-missing pre-dose value
Week 26	183	[92, 266]
Week 50	351	[267, 448]
Week 78	547	[449, the end day of the placebo-controlled period*]
Week 106	743	[645, 840]
Week 134	939	[841, 1036]
Week 162	1135	[1037, 1204]

CONFIDENTIAL

The information contained herein may not be used, disclosed, or published without the written consent of Biogen MA Inc.

Analysis visit	Target visit day	Analysis visit window
Week 182	1275	[1205, 1365]
Week 232	1625	[1535, 1715]
Week 284	1989	[1899, 2079]
Week 338	2367	≥ 2277
* The end day of the placebo-controlled period is the last day before the first infusion in LTE for subjects who enter LTE, and is the last day in study for subjects who do not enter LTE.		

Handling of missing items for scales

Please refer to the placebo-controlled SAP for the imputation method. Same method will be applied to efficacy endpoints collected in the LTE period.

3.3.2 By Visit Summary and MMRM Model

The baseline and change from baseline CDR-SB scores at each post-baseline visit will be summarized by LTE treatment group. A mixed model repeated measures (MMRM) model will be used to analyze change from baseline CDR-SB using fixed effects of LTE treatment group, time (categorical), LTE treatment group-by-time interaction, baseline CDR-SB, baseline CDR-SB by time interaction, baseline MMSE, AD symptomatic medication use at baseline (yes/no), region, and laboratory ApoE ε4 status (carrier/non-carrier). An unstructured covariance matrix will be used to model the within-patient variance-covariance errors. If the unstructured covariance structure matrix results in a lack of convergence, the heterogeneous Toeplitz covariance structure followed by the heterogeneous first-order autoregressive covariance structure will be used. The Kenward-Roger approximation will be used to estimate the denominator degrees of freedom. Visits with too few data may be excluded from the MMRM analysis and be analyzed by ANCOVA instead.

The by visit summary and MMRM analysis will be similarly performed for CDR cognitive subscore, CDR functional subscore, MMSE, ADAS-Cog 13, ADCS-ADL-MCI and NPI-10. Only the by visit summary will be performed for CDR box scores and informant-rated EQ-5D. The distribution of CDR global score will be summarized as a categorical variable at each post-baseline visit.

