3 SAMPLE SIZE JUSTIFICATION

The study's sample size is based, in part, on results from a protocol-specified interim analysis from Study 221AD103 which included 1 year data from 1, 3 and 10 mg/kg treatment groups.

A sample size of 450 subjects per treatment group (1350 in total) was planned to have approximately 90% power to detect a true mean difference of 0.5 in change from baseline CDR-SB at Week 78 between the 2 treatment groups. This power calculation was based on a 2-sided t-test assuming equal variance with a final significance level of 0.05, a standard deviation (SD) of 1.92 and a drop-out rate of 30%. The SD estimate of 1.92 for Week 78 reflected a 39% increase over the SD from the protocol-specified interim analysis of 1-year data.

The assumed true mean difference of 0.5 between the 2 treatment groups represents an approximately 25% reduction in the placebo mean change from baseline at Week 78 if the placebo mean change is estimated to be 2.

As defined in the protocol, the sample size for this study (and for the identically designed Study 221AD301) was reassessed in a blinded manner in November 2017 (approximately 3 months before enrollment completion and with about 10.6% of the data available on the primary endpoint from Studies 221AD301 and 221AD302 combined). At this timepoint, the SD of the primary endpoint was estimated based on the pooled blinded data from two studies using a modified version of Gould-Shih simple-adjustment one sample variance (Zucker et al. 1999):

$$s_{adj}^2 = s_{os}^2 - \frac{2N}{9(N-1)} \delta^2,$$

where N denotes the number of subjects included in the analysis for blinded sample size re-estimation (subjects with both baseline and Week 78 CDR-SB available at the time of sample size re-estimation), δ is the assumed true treatment effect (same treatment effect assumed for both the high dose group and low dose group in this analysis), and s_{os}^2 is the unadjusted one sample variance of the primary endpoint estimate from the pooled blinded data.

As a result of this analysis, the sample size has been increased from 1350 to 1605 (450 to 535 per treatment group) to assure adequate power for detecting a mean treatment effect of 0.5.

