At the end of the double-blind, placebo-controlled treatment period, subjects who meet the extension entry criteria may enter a long-term safety and efficacy extension period, with all subjects receiving aducanumab approximately every 4 weeks (up to a total of 65 doses over 5 years). The treatment group for the LTE period will be assigned at the same time as the randomization for the placebo-controlled period, regardless of whether a subject entering the LTE period or not. Subjects who are assigned to the placebo group during the placebo-controlled period will be assigned to 1 of 2 active treatment groups in a 1:1 ratio (aducanumab low dose: aducanumab high dose) and randomization will be stratified by their ApoE ε4 carrier status; for those who enter the LTE period, aducanumab will be titrated for up to 6 doses prior to reaching the target dose following the same schedule described for the placebo-controlled period. Subjects who are assigned to either aducanumab low dose or aducanumab high dose group in the placebo-controlled period will continue in the same treatment group for the LTE period; those who enter the LTE period will maintain the dosing scheme outlined in the protocol at the time of transition from the placebo-controlled period to the LTE period (e.g. subjects who are on stable dosing in the placebo-controlled period will continue on the same dose, subjects who are on a titration regimen during the transition will continue to titrate into the LTE period, and ApoE ε4 carrier subjects who are enrolled in the LTE and randomized to the high-dose group prior to implementation of version 4 of the protocol will be allowed to titrate to 10 mg/kg). Aducanumab will be titrated for up to 6 doses prior to reaching the target dose for the late start subjects as shown in Table 2 and Figure 1.

CONFIDENTIAL

The information contained herein may not be used, disclosed, or published without the written consent of Biogen MA Inc.

Table 2: Dosing Scheme for Aducanumab by Treatment Group and ApoE ε4 Carrier Status: Long-Term Extension Period

Doses (every 4 weeks)		1	2	3	4	5	6	7- EOS	
LTE Treatment Group	LTE Treatment Group Stratified by ApoE Status ¹	Dose (mg/kg)							
Early Start High Dose	Early Start High Dose – ApoE ε4 (+)	10							
	Early Start High Dose – ApoE ε4 (-)	10							
Early Start Low Dose	Early Start Low Dose – ApoE ε4 (+)	3							
	Early Start Low Dose – ApoE ε4 (-)	6							
Late Start High Dose	Late Start High Dose – ApoE ε4 (+)	1	1	3	3	6	6	10	

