2.2 Study Schematic

Figure 1: Study Design

ApoE ε4 +/- = apolipoprotein E4 positive/negative; FU = follow-up; P = placebo; R = randomization date.

*Subjects who are assigned to placebo during the placebo-controlled period are randomized in a 1:1 ratio to high and low dose aducanumab treatment (stratified by their ApoE ε4 carrier status) for the long-term extension period on Study Day 1.

CONFIDENTIAL

The information contained herein may not be used, disclosed, or published without the written consent of Biogen MA Inc.

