For the ¹⁸F-florbetapir amyloid PET analysis population, an MMRM model will be used to analyze change from baseline SUVR for each target ROI with cerebellum as the reference region for all the visits in the placebo-controlled and LTE period. Fixed effects of the model will include LTE treatment groups, visit, treatment group-by-visit interaction, baseline SUVR (continuous), baseline SUVR by visit interaction, baseline MMSE (continuous), laboratory ApoE ε4 status (carrier and non-carrier), and baseline age (continuous). Visit and treatment group will be treated as categorical variables in the model along with their interactions. An unstructured covariance matrix will be used to model the within-patient variance-covariance errors. If the unstructured covariance structure matrix results in a lack of convergence in any of the parameters, the heterogeneous Toeplitz covariance structure followed by the heterogeneous first-order autoregressive covariance structure will be used for all the parameters. The Kenward-Roger approximation will be used to estimate the denominator degrees of freedom. Adjusted means for each treatment group, pairwise adjusted differences for the comparisons, 95% confidence intervals for the differences and associated p-values will be presented at each visit. Visits with too few data may be excluded from the MMRM analysis and be analyzed by ANCOVA instead. The same MMRM model will also be used to analyze the change from baseline SUVR for the composite ROI with each of the reference regions. No multiple comparison adjustment will be used for amyloid PET analysis.

Visit Windows for by visit analyses

CONFIDENTIAL

The information contained herein may not be used, disclosed, or published without the written consent of Biogen MA Inc.

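### The LTE models fit separate placebo-period means to two randomised halves of one placebo arm: valid and unbiased, but it gives away precision that a common pre-LTE placebo mean would recover at almost no cost

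*SAP*

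**What the plan says.** The LTE SAP makes four statements that matter here.

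- **Assignment (section 2.1).** Placebo subjects "will be assigned to 1 of 2 active treatment groups in a 1:1 ratio". Section 2.2 dates this to the start of the trial: they are randomised to a dose group "for the long-term extension period on Study Day 1". Table 1 gives both halves saline throughout the placebo-controlled period.
- **Data (section 3.3.1).** The efficacy analysis uses the ITT population, and "data from both the placebo-controlled and LTE periods will be included". The two comparisons are early start against late start within each dose. The Week 78 window closes on the day before the first LTE infusion, so no LTE dosing falls inside it.
- **CDR-SB model (section 3.3.2).** The MMRM is fitted "using fixed effects of LTE treatment group, time (categorical), LTE treatment group-by-time interaction". The same model is applied to the CDR subscores, MMSE, ADAS-Cog 13, ADCS-ADL-MCI and NPI-10. Visits with too few data may be moved to ANCOVA.
- **PET model (section 3.4.4).** "Fixed effects of the model will include LTE treatment groups, visit, treatment group-by-visit interaction".

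Neither model constrains the late-start groups before the LTE. The placebo-controlled SAP (sections 4.3.1 and 4.3.2.1) keeps placebo as one group for the primary test. Display A in LTE Appendix 4.1 has a late-start total column, but that column does not alter the fitted model.

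**The concern.** A full group-by-time interaction spends separate parameters on two means that randomisation makes equal. At the placebo-period visits, each active arm of about 535 is compared with about 267 placebo subjects although about 535 are in the dataset. Through the within-subject correlation, some of that lost precision carries into the first LTE visits, where the long-term question lies.

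The LTE report will also show two model-based placebo estimates at Week 78, neither of which need match the single estimate in the placebo-controlled report. At stake are the efficiency and clarity of a tertiary analysis.

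**Working it through.** **Inputs from the documents.** Placebo-controlled SAP section 3: "A sample size of 450 subjects per treatment group (1350 in total) was planned to have approximately 90% power". The target is a 0.5-point CDR-SB difference at Week 78, tested by a two-sided equal-variance t-test with alpha 0.05, SD 1.92 and drop-out 30%; the arms were later raised to 535 each. LTE SAP section 2.1: 1:1 split of placebo, so 535/2 = 267.5 per half.

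**Assumptions, because the plan gives no figure.** Correlation between visits 0.5 to 0.9, either constant over time or decaying (the stated value then applies across 28 weeks); SD constant at 1.92; retention either complete or 90, 80, 70, 55, 45, 40 and 35% at Weeks 26, 50, 78, 106, 134, 162 and 182.

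**1. The plan's own figure.** n = 2 × 1.92² × (1.960 + 1.282)² / 0.5² = 310 evaluable per arm; 310 / 0.70 = 443, against 450 stated. With 450 × 0.70 = 315 evaluable, power is 90.5%. The stated figure is reproduced, so the inputs are used as given. The LTE SAP states no power or precision of its own.

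**2. Placebo-period visits.** Let n be the size of an active arm.

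- As planned: variance = SD² × (1/n + 2/n) = 3 SD²/n.
- One placebo mean: variance = SD² × (1/n + 1/n) = 2 SD²/n.
- SE ratio = √(3/2) = 1.225, whatever the SD, given equal dropout. Equivalently, the common mean cuts variance by 33% and SE by 18%.
- At Week 78 with 30% dropout (374.5 against 187.25 or 374.5): SE 0.172 falls to 0.140. With no dropout: 0.144 falls to 0.117.

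The ratio applies equally to PET at Weeks 26 and 78.

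**3. LTE visits.** Separate late-start means are needed here because the doses differ. With complete data and one informative earlier visit at correlation ρ, the constraint lowers the variance from 3 SD²/n to (3 − ρ²) SD²/n, so the SE ratio is √(3/(3 − ρ²)): 1.044 at 0.5, 1.093 at 0.7, 1.170 at 0.9, and 1.00 at zero.

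Generalised least squares for four groups and seven visits gives these ratios (planned SE / SE with common placebo mean):

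| Correlation | Retention | Week 106: ρ = 0.5, 0.7, 0.9 | Week 182: ρ = 0.5, 0.7, 0.9 |
|---|---|---|---|
| Constant | Complete | 1.069, 1.121, 1.186 | 1.069, 1.121, 1.186 |
| Constant | Falling | 1.050, 1.095, 1.168 | 1.035, 1.073, 1.149 |
| Decaying | Complete | 1.044, 1.093, 1.170 | 1.001, 1.012, 1.086 |
| Decaying | Falling | 1.035, 1.076, 1.151 | 1.000, 1.006, 1.053 |

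As an SE reduction (1 − 1/ratio), Week 106 averages about 5% at ρ = 0.5 (range 3 to 6%) and about 14% at ρ = 0.9 (13 to 16%). At Week 182 with decaying correlation and falling retention it is 0 to 5%.

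**4. Gap between the two placebo estimates at Week 78.** The expected gap is zero. Its SD is 1.92 × √(2/267.5) = 0.166 with no dropout and 1.92 × √(2/187.25) = 0.198 if only the 70% observed contribute; 95% ranges ±0.33 and ±0.39. The MMRM recovers part of the missing information. The half-against-half variance is 4 SD²/n, so the planned-model SE at Week 78 can be scaled by √(4/3): with constant correlation 0.5 and 0.9 and falling retention, 0.166 and 0.155 become 0.192 and 0.179. The gap SD therefore lies between about 0.17 and 0.20.

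**The case against.** The saturated model is standard and valid. It causes no bias and no type I error problem, the endpoints are tertiary, and section 3.3.1 makes no multiplicity claim. The largest gain falls at Weeks 26, 50 and 78, where the placebo-controlled SAP already compares each dose with the whole placebo arm. All of this stands, and it limits the point to efficiency and presentation.

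Three stronger readings might be inferred, and the documents support none of them.

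- **Every early-versus-late comparison is materially less precise.** This is assured only at the placebo-period visits. Later it depends on a correlation that the plan does not state, it can vanish by Week 182, and it does not apply to a visit moved to ANCOVA.
- **The two placebo curves conflict.** They estimate the same mean without bias and differ only by sampling error.
- **The trial's main result is weakened.** The primary test uses the undivided placebo arm under a separate plan.

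Two further objections also stand. Recoding the model alone would leave the by-visit summaries split into four groups, so the presentation text must change too. And although equality of the means needs no new assumption, the post-switch gain leans on one covariance matrix shared by all groups, including after late-start subjects change treatment. The plan already makes that assumption, but the constrained model relies on it more.

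**Conclusion.** The point holds as an inefficiency in a tertiary analysis. At the placebo-period visits the planned standard errors are 22% larger than they need be; this follows from the 1:1 split alone, given equal dropout. At Week 106 the avoidable loss is modest: a common mean lowers the SE by about 5 to 14% for assumed correlations of 0.5 to 0.9. Later it shrinks if correlation decays, possibly to nothing by Week 182. No PET figure was worked out for the LTE visits. The duplicate placebo estimates at Week 78 will typically differ by a few tenths of a CDR-SB point or less, which is visible beside a design effect of 0.5 but is only chance. Because the equality holds by randomisation, the gain is close to free and worth taking.

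**What to change.** - **Sections 3.3.2 and 3.4.4:** constrain late-start low and late-start high to a common mean at the placebo-period visits (Weeks 26, 50 and 78; for PET, Weeks 26 and 78). Keep four separate group means from the first LTE visit. In practice this is one recoded class variable with three levels (placebo, low, high) before the LTE and four afterwards. Keep all other terms and both planned comparisons.
- **Sections 3.3.1 and 3.3.2:** state that one placebo curve and by-visit summary, labelled late-start total, is presented through Week 78, with the four groups shown from the first LTE visit. Display A already has the column.

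The cost is a sentence in each model section, a short edit to the presentation text, and the matching change to the contrast statements. No data are added or lost, and the placebo-controlled SAP does not change.

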3.4 Amyloid PET analysis

3.4.1 Amyloid PET substudy

Please refer to the placebo-controlled SAP.

3.4.2 Amyloid PET regions-of-interest and reference regions

Please refer to the placebo-controlled SAP.

3.4.3 Amyloid PET Analysis Population

Please refer to the placebo-controlled SAP.

3.4.4 By Visit Summary and MMRM Model

All the analyses will be presented by LTE treatment group (early start low dose, early start high dose, late start low dose, late start high dose). The following two comparisons will be evaluated for amyloid PET SUVR in the LTE period:

- The early start low dose compared with the late start low dose;
- The early start high dose compared with the late start high dose.

The baseline and change from baseline amyloid PET SUVR values will be summarized by LTE treatment groups by visit for all the visits in the placebo-controlled and LTE period for each of the target ROIs using cerebellum as the reference region for each of the amyloid PET analysis populations. In addition, the baseline and change from baseline amyloid composite ROI values will be summarized by LTE treatment groups by visit for each reference regions for each of the amyloid PET analysis populations.

For the ¹⁸F-florbetapir amyloid PET analysis population, an MMRM model will be used to analyze change from baseline SUVR for each target ROI with cerebellum as the reference region for all the visits in the placebo-controlled and LTE period. Fixed effects of the model will include LTE treatment groups, visit, treatment group-by-visit interaction, baseline SUVR (continuous), baseline SUVR by visit interaction, baseline MMSE (continuous), laboratory ApoE ε4 status (carrier and non-carrier), and baseline age (continuous). Visit and treatment group will be treated as categorical variables in the model along with their interactions. An unstructured covariance matrix will be used to model the within-patient variance-covariance errors. If the unstructured covariance structure matrix results in a lack of convergence in any of the parameters, the heterogeneous Toeplitz covariance structure followed by the heterogeneous first-order autoregressive covariance structure will be used for all the parameters. The Kenward-Roger approximation will be used to estimate the denominator degrees of freedom. Adjusted means for each treatment group, pairwise adjusted differences for the comparisons, 95% confidence intervals for the differences and associated p-values will be presented at each visit. Visits with too few data may be excluded from the MMRM analysis and be analyzed by ANCOVA instead. The same MMRM model will also be used to analyze the change from baseline SUVR for the composite ROI with each of the reference regions. No multiple comparison adjustment will be used for amyloid PET analysis.

Visit Windows for by visit analyses

CONFIDENTIAL

The information contained herein may not be used, disclosed, or published without the written consent of Biogen MA Inc.

For amyloid PET by visit summaries and MMRM models, the analysis visit should be defined using visit windows (see Table 4 below). The rationale is to use the same analysis visit windows as for the efficacy endpoints for the visits that the efficacy endpoints are also collected. Since the visit for the efficacy measurements is on Week 134, while the visit for amyloid PET measurements is on Week 132, the start of the analysis visit window for Week 132 amyloid PET is 2 weeks earlier than that for efficacy, while the same end of the analysis visit window as Week 134 is used to be conservative. If there is more than 1 value in the same analysis visit window (>1 value for the same analysis visit) for a certain parameter for a subject, then the closest record to the target visit day will be used for the by visit analysis. If they are with the same distance from the target visit day, then the record with the later time will be used for the by visit analysis.

Table 4. Visit Windows for amyloid PET data

Analysis visit *	Target visit day	Analysis visit window
Baseline	1	Most recent non-missing pre-dose value
Week 26	183	[92, 266]
Week 78	547	[449, the end day of the placebo-controlled period ¹]
Week 132	925	[827, 1036]
Week 182	1275	[1205, 1365]
Week 260	1821	[1731, 1911]
Week 338	2367	≥ 2277
* Analysis visit is the visit at which the specific week started. 1. The end day of the placebo-controlled period is the last day before the first infusion in LTE, and is the last day in study for subjects who do not enter LTE. 2. The start day of the LTE period is the day of first infusion in LTE period.		

